PrEP services and HIV risk, based on self-reported risk behaviors and assessed for PrEP eligibility as standard of care. Those who are interested are referred to the PrEP nurse for discussion and initiation. After being started on PrEP by the nurse, potential participants will be approached by study staff and receive information regarding the study and undergo eligibility assessment. This form will include all data relevant for determining eligibility; no identifying information will be included on this form. If eligible and interested in participation, potential participants will undergo study consent, enrollment, and randomization procedures (see [Section 6.1](#)). Systems navigators will engage cisgender men randomized to the intervention arm at this point.

A sample of the assent and consent forms can be found in Appendices V and VI. If during the eligibility assessment, they are found to be ineligible, recruitment will be discontinued, and participants will be dismissed.

Throughout enrollment procedures, study staff will emphasize that enrollment in the trial does not require a commitment to use of PrEP throughout the follow-up period.

Participants will also be reminded that study remuneration is being provided at the designated quarterly study visits, not as part of their scheduled PrEP care.

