8.2.1 Primary Objective(s) and Endpoints

8.2.1.1 To assess the effect of a systems-navigator facilitated HIV prevention package on PrEP persistence among heterosexual cisgender men seeking STI clinical services in Lilongwe, Malawi at 26 weeks.

Consistent with this primary study objective, the following endpoint(s) will be assessed: Persistent PrEP use across all three modalities (LAI, daily oral, or event-driven PrEP), where persistence is defined as adherence to any PrEP modality through 26 weeks, comparing proportions in intervention and control arm participants.

- (LAI) receive on-time injections (+/- 7-day window for the first injection and 14-day window thereafter)
- (Daily Oral) have protective PrEP concentration detected at designated study follow-up visits, based on intraerythrocytic TFV-DP collected as DBS; TFV-DP concentrations associated with ≥ 4 doses/week will be classified as adherent.

- (Event-driven) self-reported PrEP adherence (2+1+1), in the past 30 days, assessed through self-report of PrEP use and sex acts at study follow-up visits, and intraerythrocytic TFV-DP concentrations.

8.2.1.2 To assess acceptability and barriers of implementing a systems-navigator delivered HIV prevention package among key stakeholders in the clinic and heterosexual cisgender men initiating PrEP at STI clinics.

Consistent with this primary study objective, the following endpoint(s) will be assessed among participants in the intervention arm only:

- Engagement with system navigators:
 - Overall: Proportion of intervention arm participants engaged by systems navigator within 7-days of enrollment visit (defined as any contact, i.e. text exchange, in-person communication)
 - Overall: Proportion of intervention arm participants engaged by systems navigators at least once after the initial engagement during the first 26 weeks following initiation of PrEP.
 - Overall: Proportion of intervention arm participants with attempted engagement by systems navigators at least once after the initial engagement during the first 26 weeks following initiation of PrEP.
 - Overall: Mean (standard error) number of contacts (text, telephone call, home visit, other) with intervention arm participants made with systems navigators (mean contacts per participant) during first 26 weeks following initiation of PrEP.
- Uptake of self-test/pill pack (“re-start” kit) among those to whom it is distributed (through end of study participation):

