8.2.3 Exploratory Objectives and Endpoints

8.2.3.1 To assess prevention-effective PrEP use among heterosexual cisgender men initiating PrEP at STI clinics

Prevention-effective PrEP use evaluates PrEP use in the context of ongoing HIV risk, exploring the alignment between periods with evidence of ongoing HIV risk and protective PrEP levels. This will be assessed for participants by evaluating self-reported HIV risk behaviors, observed incident STI or HIV, and PrEP use during quarterly study follow-up visits:

- Proportion of PrEP initiators with incident STI/HIV
- Proportion of PrEP initiators who report HIV risk during study follow-up, including self-reported sexual behaviors, and HIV status of partners
- Proportion of PrEP initiators who have target PrEP concentrations (oral) or on-time receipt (LAI) during periods of potential HIV risk based on incident HIV/STI, self-reported sexual behaviors, and HIV status of partners.
- Proportion of PrEP initiators who discontinue PrEP (based on self-report or medical record review)
- Proportion of sex acts with appropriate PrEP dosing (before and after each act) in 14- and 30-day recall periods, among PrEP initiators endorsing event-driven PrEP use

8.2.3.2 To assess PrEP modality preferences among heterosexual cisgender men initiating PrEP at STI clinics.

We will assess proportion of cisgender men selecting each of the available PrEP options at enrollment, and examine any changes in PrEP modality selection during study follow-up.

8.2.3.3 To assess the effect of a systems-navigator facilitated HIV prevention package on PrEP persistence among heterosexual cisgender men seeking STI clinical services in Lilongwe, Malawi, at 39 and 52 weeks.

Consistent with this exploratory objective, we will assess all PrEP use outcomes described in [Section 8.2.2](#) for subset of participants who are eligible for extended follow-up based on enrollment date, extending to 39 weeks or 52 weeks.

8.2.3.4 To quantify costs and resources necessary to develop and integrate a systems-navigator delivered HIV prevention package into an urban STI clinic, informing future cost-effectiveness model development.

Consistent with this exploratory study objective, the following endpoint(s) will be assessed:

- cost quantification following an ingredients-based micro-costing approach, including costs associated with training and time-and-motion evaluation of systems navigation activities including counseling and tracing.

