8.3 SAMPLE SIZE

For our HIV seronegative PrEP initiation participant population, we expect to enroll approximately 200 heterosexual cisgender males. We assume 10% loss to follow-up through 26 weeks. As a pilot study, the sample size is chosen to provide reasonable precision for assessing the primary endpoints and informing future studies. We chose a

2:1 randomization to intervention and SOC to maximize our ability to assess acceptability of the intervention.

Based on previous studies, we expect persistent PrEP use under standard of care (SOC) is 40% at 26 weeks. The targeted difference in persistent PrEP use at 26 weeks between the intervention and the standard of care arm is 15%-35%. Table 1 gives the two-sided 95% confidence intervals for the true proportions of persistent PrEP use (a binary endpoint) separately for two arms. This is a pilot study seeking to rapidly evaluate indication of an effect signal that would suggest potential benefit of systems navigation to inform a future larger study. Our sample size, selected to quickly enroll and answer this important and timely knowledge gap, will be sufficient to identify a minimum detectable RD of 0.22 assuming 80% power and 5% alpha level, and RD of 0.25 assuming 90% power and 5% alpha level.

Table 2: 95% confidence intervals for the true proportions of persistent PrEP use at 26 weeks separately for two arms, given the total sample size of 200 and assuming 10% loss to follow-up (a working sample size of 180)

Proportion of persistent PrEP use under SOC	Proportion of persistent PrEP use under intervention with varying risk difference (RD)				
	RD=0.15	RD=0.2	RD=0.25	RD=0.3	RD=0.35
(0.28, 0.52)	(0.46, 0.64)	(0.51, 0.69)	(0.56, 0.74)	(0.62, 0.78)	(0.67, 0.83)

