8.5 STATISTICAL ANALYSIS

8.5.1 Primary Analyses

Effect of intervention on persistent PrEP use

Comparison of persistent PrEP use will be performed on all enrolled participants during the first 26 weeks of study follow-up. Participants may choose to switch PrEP modalities during study follow-up; persistence to each modality will be assessed during the follow-up time when the participant reports using that modality, using a combination of self-report and clinic records. Only those who are retained on study at the end of 26 weeks will be considered to have reached the persistence endpoint. Data will be presented in a two-by-two table in which each participant is classified as persistent/non-persistent to PrEP. A Z-test based on asymptotic normality will be used to compare persistent PrEP between the intervention and the SOC arm.

Acceptability and barriers

For binary endpoints, the number will be tabulated, its specified proportion will be calculated, with variance calculated under binomial distribution. For continuous endpoints, its mean, median, standard deviation, quantiles and range will be calculated. Qualitative analyses are described separately ([Section 8.6](#))

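### The primary Z-test is valid but uses neither the age stratum nor the PrEP modality at initiation; stratifying on both could gain precision at almost no cost

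*Protocol*

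**What the plan says.** - **Primary test (Protocol 8.5.1).** Each participant is classed as persistent or not in a two-by-two table, and "A Z-test based on asymptotic normality will be used to compare persistent PrEP between the intervention and the SOC arm". No stratum or covariate is named. The same section allows switching and judges persistence by the modality in use at the time.
- **Order of events (4.3).** "After being started on PrEP by the nurse, potential participants will be approached by study staff"; eligibility, consent and randomisation follow. Section 4.1 likewise has PrEP prescribed before enrolment.
- **Endpoint (8.2.1).** The outcome is "Persistent PrEP use across all three modalities (LAI, daily oral, or event-driven PrEP"). Injectable users are judged on injection timing, daily oral users on drug concentration, and event-driven users on self-report together with concentration.
- **Modality is recorded (8.2.3.2).** "We will assess proportion of cisgender men selecting each of the available PrEP options at enrollment".
- **Randomisation (8.1).** Stratified by age only (15-25, >25), because both baseline persistence and the intervention effect are expected to differ by age.
- **Power (8.3).** "we expect persistent PrEP use under standard of care (SOC) is 40% at 26 weeks"; the trial claims a "minimum detectable RD of 0.22 assuming 80% power and 5% alpha level" and an "RD of 0.25 assuming 90% power and 5% alpha level".

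**The concern.** Modality at initiation cannot be affected by the arm, so it is a legitimate adjustment variable. There is reason to expect that it predicts the outcome: the first success rule depends on it, and section 1.2 suggests that longer-acting agents may ease the adherence problems of oral PrEP. If it does predict persistence, a chance difference between arms in the mix of starters moves the crude risk difference for reasons unrelated to navigation. Age meets the same test on firmer textual ground: the protocol expects it to matter and balances on it, yet the stated test does not use it.

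Precision is what is at stake. The targeted difference starts at 0.15, but 80% power is claimed only from 0.22, so the lower part of the target range is underpowered.

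**Working it through.** **Inputs from the protocol.** SOC persistence 0.40; 180 evaluable participants, that is 60 SOC and 120 intervention; 5% alpha, two-sided (8.3 says so for the intervals, "two-sided 95% confidence intervals for the true proportions of persistent PrEP use", and the power figures match it). **Assumed, because the protocol gives none:** persistence by modality, the mix of starters, a constant risk difference (RD) across modalities, and no switching.

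**Step 1: reproduce the stated power.** Power = Φ[(RD − 1.96·SE₀)/SE₁], with SE₀ = √[p̄(1−p̄)(1/60+1/120)] and SE₁ = √[p₀(1−p₀)/60 + p₁(1−p₁)/120].
- RD 0.22: p̄ = (24+74.4)/180 = 0.547, SE₀ = 0.0787, SE₁ = 0.0772. Power = Φ[(0.22−0.1543)/0.0772] = Φ(0.851) = 80.3%.
- RD 0.25: power 89.5%.
- Solving for RD gives 0.219 at 80% and 0.252 at 90%. Both stated figures stand, and they rest on the unadjusted test.
- The same formula gives 47.5% at RD 0.15 and 72.1% at RD 0.20.

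**Step 2: variance due to chance imbalance in modality.** With two modalities, share s and gap g, this part is s(1−s)g²(1/60+1/120). The total crude variance at RD 0.22 is 0.0772² = 0.00596. Power is from 20,000 simulated trials per row, comparing the crude Z-test with a CMH test stratified by starting modality.

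| SOC persistence | Share of second modality | Imbalance part | Share of variance | Power, crude → stratified |
|---|---|---|---|---|
| 0.35 / 0.45 | 50% | 0.00006 | 1% | 81.0% → 81.1% |
| 0.30 / 0.50 | 50% | 0.00025 | 4% | 80.3% → 81.6% |
| 0.25 / 0.55 | 50% | 0.00056 | 9% | 80.4% → 84.0% |
| 0.20 / 0.60 | 50% | 0.00100 | 17% | 80.8% → 87.0% |
| 0.34 / 0.64 | 20% | 0.00036 | 6% | 80.6% → 82.3% |

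The square root of the imbalance part, 0.008 to 0.032, is the SD it contributes to the estimated RD, against a total SE of 0.077. At a 50% share, the between-arm difference in share has SD √(0.25×0.025) = 0.079 and exceeds 10 points in about 21% of trials.

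**Step 3: all enrolled, three modalities.** 8.5.1 analyses everyone enrolled, about 67 and 133. Assume a daily/event-driven/injectable mix of 50/20/30% and RD 0.20. The variance share is the between-modality variance of persistence × (1/67+1/133 = 0.02244), divided by the crude variance.
- 30/45/60%: 0.0171×0.02244/0.00541 = 7%; simulated power 77.8% → 79.8%.
- 25/45/70%: 0.0381×0.02244/0.00541 = 16%; simulated power 77.2% → 83.0%.
- 35/40/50%: 0.0042×0.02244/0.00539 = 2%; no material gain in power.

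**Step 4: validity.** Under no effect, the Step 2 simulations gave type I error of 4.8-5.1% for the crude test and 4.9-5.2% for the stratified test. Both estimates centred on the true RD.

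**Step 5: cost if nothing is prognostic.** At 67/133, RD 0.20 and the Step 3 mix, stratifying by a non-prognostic modality moved power from 76.8% to 76.4%. A further check of 40,000 trials crossed modality with two equal age groups (an assumption), with persistence 40% in every cell. It gave 77.5% crude, 76.9% by modality and 76.3% by the six crossed cells. The cost is about half a point for modality and about one point for the full crossing.

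**The case against.** The strongest reply is that nothing here is wrong. An unadjusted comparison is acceptable for a pilot looking for a signal, the sample size was computed for that test, and covariate adjustment is often left to the SAP, which is not shown. The validity part stands in full. The SAP part stands only partly: section 8.2 defers endpoint definitions to the SAP, but 8.5.1 itself names the primary test, so an SAP that changed it would depart from the protocol.

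The second reply is that the gain may be very small, and this also stands. Section 1.2 says injectable PrEP was not available at the time of writing and that no prior studies document adherence to it in heterosexual men. If it arrives three-quarters of the way through accrual and 55% then choose it, permuted blocks (size 6 assumed) already balance much of the modality mix over calendar time. A simulation of that case (SOC 30% against 60%, RD 0.20) showed only about 2% less variance, with power 77.0% → 79.0%. With arrival at mid-accrual the reduction was about 5%.

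A reader might also infer more than the documents support:
- *That the crude result is biased or the test invalid.* Chance imbalance is already inside the crude standard error.
- *That starting modality fixes the persistence rule throughout.* Switching is allowed and the rule follows the modality in use, so it sets only the first rule. Switching would also weaken its prognostic value.
- *That modality is the strongest baseline predictor.* The protocol gives no rates by modality; the predictor it names when choosing strata is age.

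**Conclusion.** The point holds as an efficiency improvement. The primary Z-test is valid and the stated detectable differences are right. It leaves unused a randomisation stratum that the protocol expects to matter and a pre-randomisation variable that the trial already records.

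The gain from modality runs from about zero to roughly 6-17% less variance and 2-6 power points. The upper part needs gaps of 30 to 45 points and mixed uptake at initiation. All rates and mixes are assumptions, and switching, which the main calculations omit, would probably reduce the gain. The gain from age cannot be sized, because the protocol gives no persistence by age. The case for acting is the asymmetry: a possible gain of several power points against a loss of about half a point for modality, or about one point for the full crossing.

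**What to change.** In 8.5.1, and in the SAP to match:

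1. Make the primary estimate a Mantel-Haenszel risk difference with its 95% CI and the CMH test, stratified by age group (15-25, >25) and by PrEP modality at initiation, taken from the record made before randomisation. Never use modality after switching, which is a post-randomisation variable.
2. Keep the crude two-by-two table and Z-test as supportive.
3. State in advance, without reference to arm or outcome, a minimum number of starters below which modality strata are collapsed. Event-driven then merges with daily oral. If injectable starters fall below the minimum, drop modality and stratify by age alone, since injectable has no natural group to merge into.

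The power statement in 8.3 can stay as the figure for the unadjusted test. The cost is wording only: no new data, visits or participants. It should be settled before outcome data are seen by arm.

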8.5.2 Secondary Analyses

Feasibility of a future randomized controlled trial

Secondary data analysis will tabulate the number of each endpoint observed during the study. For binary endpoints, its percentage of the total enrolled participants will be calculated, with variance calculated under binomial distribution. For continuous endpoints, its mean, median, standard deviation, quantiles and range will be calculated. Z-tests will be used to compare endpoints between arms.

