3.1 PARTICIPATING SITE

Bwaila Sexually Transmitted Infection (STI) Clinic is located in Lilongwe, Malawi. Bwaila STI Clinic is an affiliate of UNC Project Malawi. UNC Project Malawi is the official CRS for this study and will be registered to the protocol and responsible for data management and LDMS.

The Bwaila STI clinic is located within the Bwaila Hospital, a free secondary level public facility. The Bwaila hospital is in a busy town area in the center of the Lilongwe city, the capital city of Malawi. It has a catchment population of about 130,000 people. At the Bwaila STI clinic, PrEP services are co-located within the STI clinic, an integrated program launched in November 2021. HIV testing is standard of care and is offered as a routine opt-out service. HIV status ascertainment is around 98%. All STI patients who test HIV negative may be offered PrEP. On average, the STI clinic sees about 50 HIV seronegative patients per day of whom about 45% are cisgender male. Among the seronegative patients, about 5-10% accept to start PrEP daily. Hepatitis B testing before PrEP initiation is standard of care however, clients can start PrEP and be tested later if testing is unavailable at initiation.

The UNC Project Malawi works in collaboration with a Community Advisory Board (CAB). The CAB consists of diverse members that span across all demographics including adolescents and backgrounds. The CAB meets routinely every quarter and when a need arises. Aside from the general CAB, the UNC Project Malawi CAB has an adolescent arm called the Adolescent CAB, which provides guidance on studies that involve adolescents. The protocol team held a consultative meeting with the UNC Project Malawi CAB where the members were briefed about the HPTN 112 protocol. CAB members provided feedback on the general approach of the study and guidance on how to select appropriate system navigators. In addition, the members provided guidance on the best ways for the system navigators to approach participants in their communities. In addition, the Malawi MoH Department of HIV, Viral Hepatitis and STIs provided their support for the study. Finally, the protocol team will brief the Lilongwe District Health Office Research Committee on the HPTN 112 protocol and obtain a letter of support on the same.

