6.3.1 Quarterly visits (Weeks 13, 26, 39* and 52*)

The following procedures will be conducted at each quarterly visit:

Administrative and Behavioral Procedures:

- Locator information (if location has changed)
- Behavioral risk, risk perceptions, and health assessment
 - 30-day timeline follow-back [TLFB] (sex acts and PrEP use)
 - substance use
 - mental health
 - anticipated and experienced PrEP-related stigma
 - anticipated and experienced HIV-related stigma

- gender norms
- PrEP use assessment
- HIV risk reduction counseling

Clinical Procedures:

- Symptom-driven physical examination
- Blood collection
- Urine collection

Laboratory Procedures:

- HIV rapid antibody testing
- Syphilis RPR & reflex TPPA if appropriate
- CT/NG (if >2 weeks since testing conducted at PrEP visit)
- Plasma storage
- Urine storage
- DBS storage

**A subset of participants will also have a visit at Weeks 39 and 52, if the window of study follow-up allows. Participants enrolled in the first 13 weeks of recruitment will be followed for 52 weeks and those enrolled during the first 26 weeks of recruitment will be followed for 39 weeks. The remaining participants will be followed for 26 weeks total follow-up.*

Identical procedures will occur at Weeks 13, 26, 39, and 52, with the notable exception that a subset of participants will be asked to engage in an in-depth interview during their final visit (Week 26, 39, or 52).

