8.2.2 Secondary Objective(s) and Endpoints

8.2.2.1 To assess the feasibility of a future randomized controlled trial.

Consistent with this secondary study objective, the following endpoint(s) will be assessed, considering all enrolled HIV seronegative participants:

- Calendar time to enroll 200 participants
- Proportion of participants retained at each [eligible] study visit
- Complete all study visits through 26 weeks, 39 weeks, and 52 weeks (among participants eligible for longer follow-up)
- Proportion of PrEP visits on the same day as study visits, by PrEP modality
- Proportion of participants completing 30-day TLFB at quarterly study visits
- Time to complete each study visit
- Additional time (at PrEP visits) engaging with systems navigators

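### Section 8.5.2 divides every binary feasibility endpoint by all enrolled men, contradicting the denominators in 8.2.2.1 for Week 39/52 retention and completion and for same-day PrEP visits

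*Protocol*

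**What the plan says.** Feasibility of a future randomized trial is the only secondary objective. Section 8.2.2.1 lists its endpoints, and three carry their own denominator:

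- Retention is given as "Proportion of participants retained at each [eligible] study visit", so its base is the men due at that visit.
- The completion endpoint narrows its base for the two later time points to men whose enrolment date allows them that far: "Complete all study visits through 26 weeks, 39 weeks, and 52 weeks (among participants eligible for longer follow-up").
- Same-day attendance has the visit as its unit and is split by type of PrEP: "Proportion of PrEP visits on the same day as study visits, by PrEP modality".

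Section 6.3.1 determines who can contribute to the later visits: "Participants enrolled in the first 13 weeks of recruitment will be followed for 52 weeks". Men recruited in the first 26 weeks go to Week 39, and everyone else stops at Week 26 by design.

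Section 8.5.2 then gives a single rule for the analysis: "For binary endpoints, its percentage of the total enrolled participants will be calculated, with variance calculated under binomial distribution". The same paragraph adds: "Z-tests will be used to compare endpoints between arms". It makes no exception for visits that only some men are scheduled to attend, or for an endpoint whose unit is a visit.

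The parallel sentence for the acceptability endpoints in 8.5.1 is worded differently. There, for each binary endpoint, "its specified proportion will be calculated", which leaves each endpoint its own denominator.

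**The concern.** The endpoint definitions and the analysis rule cannot both be followed. Under 8.5.2, a man recruited in week 30 of accrual stays in the Week 39 and Week 52 denominators although the protocol never schedules those visits for him. He counts the same as a man who was due and did not attend. The reported percentage then mixes retention with the speed of accrual and cannot exceed the share of men recruited early enough.

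For same-day attendance, the numerator counts visits. Dividing it by the number of men does not give a proportion, and the split by modality loses its base.

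Retention beyond 26 weeks is a direct planning input for the larger trial that this pilot is meant to inform. Section 8.4 sets an overall retention target of 90%, and percentages on the wrong base would be read against it. The between-arm tests on these endpoints inherit the same denominator.

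**Working it through.** The protocol states no computed figure for these endpoints, so there is none to reproduce. The check asks what the 8.5.2 rule reports when the 8.2.2.1 quantity is known.

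**Inputs from the protocol.** 200 men, 2:1 allocation (8.1); accrual of about 39 weeks and a 90% retention target (8.4); eligibility cut-offs at 13 and 26 weeks of recruitment (6.3.1); clinic flow of about 50 seronegative patients a day, 45% male (3.1), where "Among the seronegative patients, about 5-10% accept to start PrEP daily".

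**Assumed.** The accrual pattern, which the protocol does not give, and 90% retention among eligible men at Weeks 39 and 52.

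**Formula.** If a share s of the men is eligible for a visit and a fraction r of those is retained, 8.2.2.1 gives r and 8.5.2 gives s × r. The ceiling at r = 1 is s.

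**Uniform accrual over 39 weeks, r = 0.90**

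| | Week 39 | Week 52 |
|---|---|---|
| Eligible share s | 26/39 = 0.667 | 13/39 = 0.333 |
| Eligible men | 133.3 | 66.7 |
| Retained | 120 | 60 |
| 8.2.2.1: retained/eligible (95% CI) | 90% (85–95%) | 90% (83–97%) |
| 8.5.2: retained/200 (95% CI) | 60% (53–67%) | 30% (24–36%) |

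The intervals use p ± 1.96 × √(p(1−p)/N). For example, √(0.3 × 0.7/200) = 0.0324, so 0.30 ± 0.064.

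**Other accrual patterns (ceilings s)**

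- *Weekly rate tripling linearly over 39 weeks*, r(t) = 1 + 2t/39. Cumulative accrual is T + T²/39, which is 17.33, 43.33 and 78 at 13, 26 and 39 weeks. Ceilings: 43.33/78 = 56% (Week 39) and 17.33/78 = 22% (Week 52).
- *Clinic flow, lower end* (5-day week, men starting PrEP at the quoted rate and every starter enrolling, all assumed): 50 × 0.45 × 0.05 × 5 = 5.625 men a week, or 35.6 weeks to reach 200. Ceilings: 26/35.6 = 73% and 13/35.6 = 37%.
- *Clinic flow, upper end*: 50 × 0.45 × 0.10 × 5 = 11.25 men a week, or 17.8 weeks. Ceilings: 100% (Week 39) and 13/17.8 = 73% (Week 52).

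**Effect on the between-arm Z-test.** This is an illustration with an assumed 95% versus 80% retained among eligible men, uniform accrual, arms of 133.3 and 66.7, and pooled variance.

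- Week 39, eligible men (88.9 vs 44.4), pooled p = 0.90: z = 0.15/√(0.09 × (1/88.9 + 1/44.4)) = 0.15/0.0551 = 2.72, p = 0.006.
- Week 39, all enrolled (0.633 vs 0.533), pooled p = 0.60: z = 0.10/√(0.24 × (1/133.3 + 1/66.7)) = 0.10/0.0735 = 1.36, p = 0.17.
- Week 52, eligible men (44.4 vs 22.2): z = 0.15/0.0779 = 1.92, p = 0.054.
- Week 52, all enrolled (0.317 vs 0.267): z = 0.05/0.0687 = 0.73, p = 0.47.

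**Same-day endpoint.** Each man can contribute several PrEP visits, so even on the correct base of visits the outcomes are repeated within a man and a simple binomial variance does not apply. The protocol gives no within-man correlation and no distribution of visits per man, so neither the direction nor the size of that error can be determined.

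**The case against.** The strongest reply is that the two sections can be reconciled. The lead-in to the 8.2.2.1 list says that these endpoints consider every enrolled seronegative participant, whereas the acceptability list is confined to the intervention arm. On that reading, 8.5.2 merely names the analysis population (both arms), and the specific definition of each endpoint governs over a one-sentence summary. Section 8.2 also sends further endpoint detail to the SAP. This does not remove the conflict. The lead-in names a source population that its own bullets then narrow, while the wording of 8.5.2 is a denominator. An SAP that used the 8.2.2.1 denominators would depart from 8.5.2.

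Other parts of the reply carry more weight:

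- A careful analyst would probably divide by eligible men anyway, and the correct percentage can be recovered from counts and enrolment dates.
- No decision rule depends on Week 39 or 52 retention. Those visits are marked optional in the visit-window table, and the 10% loss assumption in 8.3 runs only to Week 26.
- The sizes rest on assumed accrual. If accrual ends within 26 weeks, Week 39 is not distorted at all.
- The 95% versus 80% contrast is an illustration, not a protocol hypothesis. At Week 52 even the correct denominator does not reach the 5% level.
- The same-day endpoint is the lesser part. A participant-based rule fits a visit-level proportion so poorly that few would apply it literally, but 8.5.2 makes no exception for it.

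**Conclusion.** The concern holds. Section 8.5.2 fixes a denominator that contradicts 8.2.2.1, and applying it gives wrong values for Week 39 and Week 52 retention and completion whenever some men are not eligible for those visits.

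Under uniform 39-week accrual, 90% retention is reported as 60% and 30%. The Week 52 ceiling is below 100% in every accrual pattern examined (22% to 73%). The Week 39 ceiling runs from 56% to 100%. The contradiction itself depends on no assumption; only its size depends on accrual. The same-day endpoint is also mis-specified, with no size claimed for the variance error.

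The effect is confined to the secondary feasibility objective. The primary analysis, the sample size and the participant-level endpoints at Weeks 13 and 26 are untouched. The text should be corrected, but the trial's main result is not at risk.

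**What to change.** In 8.5.2, replace the all-enrolled denominator with the one that 8.2.2.1 defines for each endpoint: participants eligible by enrolment date for the visit in question, and PrEP visits within modality for same-day attendance. State that the between-arm Z-tests use the same denominators. For the same-day proportion only, add that the variance will be clustered by participant.

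The cost is one reworded sentence and one added clause. No new data, visits or participants are needed.
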